Approximately 4 weeks after EOS/ET Visit, all subjects should be contacted by telephone for a safety follow-up assessment of AEs and use of any concomitant medications.

A schematic depicting the study design is presented in [Figure 1](#). A complete list of procedures and assessments for subjects is in the Schedule of Events (SOE) in [Appendix 1](#).

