#### 9.5.1.1 Adverse Events

All AEs will be coded using the most up-to-date version of the Medical Dictionary for Regulatory Activities (MedDRA) and reported to the FDA. AEs that began after the EOS visit will not be included in the safety analysis. Only TEAEs occurring post administration of RBP-6000 will be included in the safety analysis (See [Section 6.9.2](#)).

The incidence of AEs (number and percent of subjects reporting the AE at least once during the study) will be summarized for all AEs, by the relationship to IMP and by severity.

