12.0 SAFETY ANALYSES

All analyses will be conducted by Analysis Period (s) over time at each analysis visit or overall in the Safety Analysis Set. Please see definition for Analysis Period and Analysis Visit in [Section 20.1](#) and [20.2](#) respectively.

The following variables will be evaluated to assess the safety and tolerability of RBP-6000:

- Incidence of treatment-emergent adverse events (TEAEs).
- Changes in clinical laboratory results.
- Vital sign measurements.

Other Safety Variables are:

- Medical history.
- Urine pregnancy test.
- Suicidality using the C-SSRS.
- Prior and concomitant medications.
- Local injection site tolerability (e.g., injection site grading).
- Injection site pain using a subject-reported VAS.
- Weight, BMI, waist circumference, hip circumference and waist-to-hip ratio.
- Behavioral therapy.

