12.1 ADVERSE EVENTS

12.1.1 Adverse Events

Imputation rules for AE (for determination of TEAE only) start date are in Section 20.7.

Treatment-emergent Adverse Events (TEAEs)

TEAEs are those that started following the first dose of RBP-6000 and before the Treatment End Date (the maximum of the date of the end-of-study/ Early Termination (EOS/ET) visit and the date of last injection + 28 days) in this study, or were present prior to the first dose of RBP-6000 regardless of causality and increased in severity within the treatment period (defined in section 20.1) AEs include those events that are ongoing at the time a subject rolls-over from the RB-US-13-0003.

Treatment-related Adverse Events

A summary of TEAEs will be presented for the Safety Analysis Set, including the number and percentage of subjects reporting at least one TEAE, the number and percentage of subjects with the following:

- Related TEAEs
- SAEs
- Related SAEs
- TEAEs with an outcome of death
- TEAEs
- Severe TEAEs
- TEAEs leading to RBP-6000 discontinuation

A breakdown of the number and percentage of subjects reporting each TEAE categorized by SOC and PT coded per the MedDRA dictionary version 19.0 will be presented in the Safety Analysis Set. Note that counting will be by subject not by event and subjects will be only counted once within each SOC or PT.

A further tabulation of events experienced by $\geq 5\%$ of subjects by SOC and PT will be presented for the Safety Analysis Set. If there are no TEAEs experienced $\geq 5\%$ of subjects by any PT, this table will be empty.

A summary of events reported, categorized by severity, will also be provided. Subjects with multiple events within a SOC or PT will be counted under the category of their most severe event within that SOC or PT. A further tabulation of severe AE/TEAEs will be presented by SOC and PT.

Additionally, treatment-related AEs/TEAEs will be summarized by maximum severity (mild, moderate, or severe). A breakdown of severe treatment-related AEs/TEAEs by SOC and PT will be provided.

All AEs (including non-TEAEs) recorded on the CRF will be listed.

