12.1.5 Potentially Pertaining to Drug Withdrawal Symptoms

A summary of TEAEs potentially pertaining to drug withdrawal during the Treatment Period, as defined in [Appendix 1](#), will be summarized by SOC and PT for the Safety Analysis Set.

Additionally, A summary table of Adverse Events potentially pertaining to drug withdrawal during the Safety Follow-up Period will be used to tabulate AEs related to drug withdrawal symptoms in the Safety Follow-Up period after EOS/ET visit, if any.

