20.0 DATA HANDLING CONVENTIONS

20.1 REFERENCE DATES AND ANALYSIS PERIODS

There are two analysis periods in this study:

- Treatment Period (TP)
- Safety Follow-Up Period (SFU).

Treatment Period starts from Treatment Start Date and ends at Treatment End Date. Treatment Start Date (or Day 1) for a subject is the date of the first injection. Treatment End Date for a subject is the maximum of the date of the end-of-study/ Early Termination (EOS/ET) visit and the date of last injection + 28.

Safety Follow-Up Period starts from Safety Follow-Up Start Date and ends at Safety Follow-Up End Date, which are defined for all subject who have assessments in the Follow-Up period.

Safety Follow-Up Start Date for a subject is Treatment End Date +1.

Safety Follow-Up End Date for a subject is defined as the date of visit at Week 29 or unscheduled visit after the Treatment End Date (defined as above) for AE/concomitant medication reporting or lab/vital signs assessment, whichever comes later. That is, Follow-up end date is max (Follow-up Start Date, date of visit at Week 29, last unscheduled visit after the Treatment End Date to report AE/concomitant medication or to do lab/vital signs assessment, if available).

Any records collected prior to first injection date/time will be considered as Screening records. And any records collected after the Treatment End Date will be considered as Safety Follow-up records.

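### An AE that starts after an early exit but within 28 days of the last injection is treatment-emergent by onset (SAP 12.1.1) yet a follow-up record by collection date (SAP 20.1)

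*SAP*

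**What the plan says.** Five statements bear on where an AE is counted.

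- SAP 12.1.1 works by onset: "TEAEs are those that started following the first dose of RBP-6000 and before the Treatment End Date". That date is "the maximum of the date of the end-of-study/ Early Termination (EOS/ET) visit and the date of last injection + 28 days".
- SAP 20.1 gives the Treatment Period the same end date and adds that "Safety Follow-Up Start Date for a subject is Treatment End Date +1". It then closes with a rule based on collection: "any records collected after the Treatment End Date will be considered as Safety Follow-up records".
- SAP 12.0 runs all safety analyses by the periods of 20.1, either "over time at each analysis visit or overall in the Safety Analysis Set".
- SAP 12.1.5 describes its follow-up table as covering "AEs related to drug withdrawal symptoms in the Safety Follow-Up period after EOS/ET visit", which is a different starting point from 20.1.
- Protocol 9.5.1.1 sets its own limit: "AEs that began after the EOS visit will not be included in the safety analysis".

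On data collection, protocol 3.1 states that about 4 weeks after EOS/ET "all subjects should be contacted by telephone for a safety follow-up assessment of AEs and use of any concomitant medications". Protocol 3.3 requires the EOS/ET visit and the call of every dosed subject who discontinues. SAP 21.0 declares no change from the protocol's analyses.

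**The concern.** The 28-day extension in the Treatment End Date matters for subjects who leave before the depot's release period of about 28 days (protocol 5.2) has run out. For them no visit is scheduled between ET and the Treatment End Date. Unscheduled contacts apart, an AE that starts in that stretch is learned of at the telephone call. Taken literally, the collection rule in SAP 20.1 then places the AE in follow-up, although its onset makes it treatment-emergent.

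This can affect the output. In SAP Appendix 3, Table 14.3.1.1 (overall TEAE summary) carries no period in its title, while nearly all AE tables from 14.3.1.2 on are titled for the Treatment Period. If the period flag follows 20.1, one AE can be in the overall count and missing from the counts by term, severity and special-interest topic. The only AE summary planned for the follow-up period covers withdrawal-type events. Safety monitoring is part of the study's single objective, so the assignment of AEs to periods should not be left to the programmer.

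**Working it through.** The documents give no figure for this point that could be reproduced, so the check is date arithmetic.

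**Inputs.** Day 0 is the last injection and k is the day of the ET visit.
- Treatment End Date = max(k, 28) (SAP 20.1).
- Call = k + 28, with the schedule's −2/+7 day window giving k + 26 to k + 35 (protocol 3.1 and Appendix 1). The schedule agrees with this: 169 − 141 = 28 days from Injection 6 to EOS, and 197 − 169 = 28 days from EOS to the call.
- Days after ET up to and including day 28 = 28 − k.

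| ET day k | Treatment End Date | Call: earliest / nominal / latest | Days after ET through day 28 |
|---|---|---|---|
| 2 | 28 | 28 / 30 / 37 | 26 |
| 3 | 28 | 29 / 31 / 38 | 25 |
| 7 | 28 | 33 / 35 / 42 | 21 |
| 14 | 28 | 40 / 42 / 49 | 14 |
| 21 | 28 | 47 / 49 / 56 | 7 |
| 26 | 28 | 52 / 54 / 61 | 2 |
| 28 | 28 | 54 / 56 / 63 | 0 |

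For k of 3 or more the earliest permitted call is at 3 + 26 = 29 or later, so it always falls after the Treatment End Date. Only with k of 0 to 2 can a call within the window fall on or before it.

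**One event through the rules.** Take ET on day 10, onset on day 20 and the call on day 38. The Treatment End Date is max(10, 28) = 28.
- SAP 12.1.1: 20 < 28, so it is a TEAE.
- SAP 20.1, collection sentence: 38 > 28, so it is a Safety Follow-up record.
- Protocol 9.5.1.1: excluded because 20 > 10, but only if the EOS visit is taken to include the ET visit; otherwise the rule is silent here.

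**Boundary day.** SAP 12.1.1 requires a start before the Treatment End Date, while SAP 20.1 ends the period at that date. An onset on day 28 is therefore inside the Treatment Period but not a TEAE.

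**Protocol limit for completers.** The visit window allows EOS at +26 or +27 days. With EOS at +26, an AE starting on day 27 is a TEAE under SAP 12.1.1 (27 < 28) but began after the EOS visit, so protocol 9.5.1.1 leaves it out. With EOS at +27, day 28 is in the same position once the end date is inclusive.

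**Table 14.3.1.13.** Its title refers to treatment-emergent AEs during follow-up. By onset, no new AE can start both before the Treatment End Date and on or after Treatment End Date + 1. For new AEs the title fits only some other rule, such as collection date.

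**Illustration of scale (assumption).** The documents give neither a dropout rate nor an AE rate. If 5% to 30% of 300 subjects left 14 days after their last injection, the stretch would hold 15 × 14 = 210 to 90 × 14 = 1,260 person-days. Against 300 × 168 = 50,400 days that is 0.4% to 2.5%. These are days at risk, not lost AEs.

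**The case against.** The strongest reply is that the SAP already treats AEs by onset. The TEAE definition is specific, SAP 20.7 imputes AE start dates to support it, and neither uses a reporting date. The collection sentence stands beside a matching one on screening records and leads into the visit-labelling rules of 20.2, so it can be read as a rule for visit data. Medications are already split by start and stop dates in SAP 9.3. A careful programmer could well let 12.1.1 govern.

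That reading is plausible, but the SAP does not state it. The sentence is unqualified, 20.1 itself names AE reporting when it sets the follow-up end date, SAP 12.0 sends all safety analyses through those periods, and the title of Table 14.3.1.13 points the other way.

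Other parts of the reply stand, and they rule out stronger readings that a reader might infer:
- *That the protocol flatly excludes these AEs for early exits.* Protocol 9.5.1.1 names the EOS visit, protocol 9.3 ties that visit to Week 25, Day 169, and the protocol writes EOS/ET elsewhere when it means both. The conflict for early exits is conditional.
- *That AEs vanish from the report.* All AEs are listed, including those that are not treatment-emergent, and SAEs and deaths are listed for all screened subjects.
- *That the result is a bias against subjects who left because of an AE.* An AE that prompted the exit began on or before ET and is normally recorded by that visit, so it stays in the Treatment Period. Only a new AE after ET that is first learned of after the Treatment End Date is exposed.
- *That every day in the stretch is on depot.* Protocol 6.12.1 allows for surgical removal in subjects who withdraw within 14 days of an injection.

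**Conclusion.** The collection sentence in SAP 20.1 is wrong as written for AEs. Applied literally, it moves a treatment-emergent AE into follow-up when a subject leaves fewer than 28 days after the last injection and first reports the AE at the call. The consequence is a possible mismatch between Table 14.3.1.1 and the by-term tables, not a loss from the listings. The exposure per subject is exact, at 28 − k days (one day fewer while 12.1.1 keeps its strict end). The number of AEs affected cannot be derived from the documents, and the person-day range above rests wholly on assumed exit rates and timing.

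The second finding does not depend on how 20.1 is read. SAP 12.1.1 counts some AEs that begin after the EOS visit, which protocol 9.5.1.1 leaves out, and SAP 21.0 does not record the difference. This is certain for an EOS at +26 days with an onset the next day. For early exits it holds only if the EOS visit includes ET.

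**What to change.** All changes are to SAP wording.

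1. In 20.1, limit the collection rule to visit-based assessments, assigned by the date performed. Assign AEs to periods by onset date (date of worsening for AEs present before the first dose). Leave medications under 9.3.
2. Make the end date inclusive in both 12.1.1 and 20.1, so that an onset on the Treatment End Date is in the period and is a TEAE.
3. In 12.1.5, start the follow-up period at Treatment End Date + 1, as in 20.1, and drop the treatment-emergent label from the title of Table 14.3.1.13.
4. In 21.0, record that AEs with onset after the EOS visit (and after ET, if that is what the protocol means) up to last injection + 28 days are included, as an extension of protocol 9.5.1.1.

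No new data are needed. With these changes the worked event (ET day 10, onset day 20, call day 38) is a TEAE in the Treatment Period whenever it is reported. The cost is a few sentences, and a few more TEAEs may be counted.

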20.2 ANALYSIS VISITS AND OTHER DEFINITIONS

All data will be presented in listings (including unscheduled visits), however only per-protocol visits will be summarized in tables and figures. Unscheduled and scheduled assessments will be utilized in the summaries for “at any time”.

For lab values, body weight, BMI, waist circumference, hip circumference and waist-to-hip ratio, Early Termination and End-of-study results will be reported with the EOS/ET visit.

For all other assessments, occurring at the ET visit, will be mapped to the next per-protocol visit (or time point), that has not already been completed by the subject. A ET visit must not be mapped to a visit that a subject has already completed.

The closest assessment value on or before Treatment Start Date/Time will be assigned as Baseline value and then be labeled as 'Baseline' in visit window, and for assessment prior to Treatment Start Date/Time, if exists, will be labeled as 'EOS 0003' or 'Screening' per its collecting time and per SOE definition.

For subjects who have one visit-based assessment in the Safety Follow-up (SFU) period, the period of the visit will be labeled as 'Safety Follow-Up Week 29'.

Other Definitions:

Subgroups

Sex

- Male
- Female

Age Categories

- ≥ 18 to < 30
- ≥ 30 to < 45
- ≥ 45 to < 60
- ≥ 60
- ≥ 65

Race

- White
- Non-White

Baseline BMI Categories

- Under weight: 0 to $< 18.5 \text{ kg/m}^2$
- Normal: $\geq 18.5 \text{ kg/m}^2$ and $< 25 \text{ kg/m}^2$
- Over weight: $\geq 25 \text{ kg/m}^2$ and $< 30 \text{ kg/m}^2$
- Obese: $\geq 30 \text{ kg/m}^2$

20.3 DERIVED EFFICACY VARIABLES

Not applicable.

20.4 REPEATED OR UNSCHEDULED ASSESSMENTS OF SAFETY PARAMETERS

See reference rules on unscheduled assessments in [Section 20.2](#). Unscheduled assessments will be utilized in analyses “at any time” and will be listed in listings.

If there are more one assessments on one parameter at scheduled visits, the last assessment will be used for visit-based table/figure summaries.

20.5 MISSING DATE OF INVESTIGATIONAL PRODUCT

When the date of the last injection of RBP-6000 during the Treatment Period is missing for a subject in the Safety Population, all efforts should be made to obtain the date from the investigator. If it is still missing after all efforts, then the last available dosing record date will be used as the last dose date.

20.6 MISSING SEVERITY AND RELATIONSHIP TO STUDY DRUG IN ADVERSE EVENTS

If the severity is missing for an AE started on or after the date of the first dose of the investigational product, then a severity of “Severe” will be assigned.

If the relationship is missing for an AE started on or after the date of the first dose of the investigational product, then a relationship of “Related” will be assigned.

The imputed values for assessment will be used for incidence summary, while the actual values will be presented in data listings.

20.7 MISSING DATE INFORMATION FOR ADVERSE EVENTS

When the AE start date is incomplete (i.e., partially missing), then the following rules will be applied:

Missing day and month

- If the year is the same as the year of the date of the first dose of investigational product, then the day and month of the date of the first dose of investigational product will be assigned to the missing fields.
- If the year is before the year of the date of the first dose of investigational product, then December 31 will be assigned to the missing fields.

- If the year is after the year of the date of the first dose of investigational product, then January 1 will be assigned to the missing fields.

Missing month only

- The day will be treated as missing and both month and day will be replaced according to the above procedure.

Missing day only

- If the month and year are the same as the month and year of the date of the first dose of investigational product, then the day of the first dose of investigational product will be assigned to the missing day.
- If either the year is before the year of the date of the first dose of investigational product or if both years are the same but the month is before the month of the date of the first dose of investigational product, then the last day of the month will be assigned to the missing day.
- If either the year is after the year of the date of the first dose of investigational product or if both years are the same but the month is after the month of the date of the first dose of investigational product, then the first day of the month will be assigned to the missing day.

If the stop date is after the date of the first dose of investigational product, the date of the first dose of investigational product will be assigned to the missing start date

If the stop date is before the date of the first dose of investigational product, the stop date will be assigned to the missing start date

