#### **6.9.3 Performing Adverse Events Assessments**

The Investigator is ultimately responsible for assessing and reporting all AEs as outlined in the protocol. The assessment of AEs may be delegated to a medically qualified Sub-investigator, trained on this study protocol, who is listed on the FDA Form 1572 or equivalent document, and on the delegation of authority form.

AEs should be volunteered by the subject or solicited from the subject using a standard statement, obtained from examination of the subject at a site visit, or from observations of clinically significant laboratory values or special examination abnormal values. If an event assessed by one of the study scales requires intervention, or if in the opinion of the Investigator, it is clinically significant, then it will be reported as an AE. Any ongoing AEs reported in the RB-US-13-0003 study will be recorded in the eCRF for this study.

All AEs are to be assessed and recorded in a timely manner and followed to resolution or until the Investigator determines that there is not an anticipated resolution. Each AE is to be documented with reference to severity, date of occurrence, duration, treatment, and outcome. Furthermore, each AE is to be classified as being serious or non-serious. In addition, the Investigator must assess whether the AE is drug-related or not.

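### For some AEs carried over as ongoing from RB-US-13-0003, SAP 20.7 imputes the first-dose date, so known pre-dose events can be counted as TEAEs without worsening

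*SAP*

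**What the plan says.** **Carried-over AEs are in the data.** Protocol 6.9.3: "Any ongoing AEs reported in the RB-US-13-0003 study will be recorded in the eCRF for this study". Protocol 6.9.1 says the same. SAP 12.1.1, directly after its TEAE definition: "AEs include those events that are ongoing at the time a subject rolls-over from the RB-US-13-0003".

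**TEAE definition.** SAP 12.1.1 has two limbs. An AE counts if it starts after the first dose and before the Treatment End Date. An AE already present before the first dose counts only if its severity increases in the Treatment Period. SAP 12.1.1 also says that the start-date imputation in 20.7 serves only to determine TEAE status.

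**Imputation to the first-dose date.** SAP 20.7 does this in three cases:

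1. Day missing, month and year those of first dose: "then the day of the first dose of investigational product will be assigned to the missing day".
2. Day and month missing, year that of first dose: "then the day and month of the date of the first dose of investigational product will be assigned to the missing fields". A missing month alone is handled in the same way.
3. Start date missing, stop date after first dose: "the date of the first dose of investigational product will be assigned to the missing start date".

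**Imputation before the first dose.** A known earlier month gives the last day of that month ("the month is before the month of the date of the first dose of investigational product, then the last day of the month"). A known earlier year gives the end of that year ("If the year is before the year of the date of the first dose of investigational product, then December 31 will be assigned"). If the start date is missing and the AE stopped before first dose, the start takes the stop date.

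Neither 20.7 nor 12.1.1 exempts AEs carried over from RB-US-13-0003.

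**The concern.** Imputing onset to the first-dose date is a sensible default when it is unknown whether the event began before or after dosing. For an AE recorded as ongoing at the RB-US-13-0003 EOS visit, the order is known: the event came first. In the three cases above the rule overrides that knowledge and takes the event out of the limb that requires worsening.

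TEAE incidence is the first safety variable listed in SAP 12.0. There is one treatment group (SAP 6.3) and no control arm in which the same error would appear. An event moved to Day 1 would enter the overall TEAE table and, where it qualifies, the severity, relatedness, discontinuation and special-topic tables. If SAP 20.6 works from imputed dates, which it does not say, a moved event with missing severity or relationship would also default to severe or related.

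The SAP gives explicit roll-over rules for prior medications (9.3) and for laboratory reference limits (20.9). It gives none for AE onset.

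**Working it through.** The plan states no figure on this point, so there is none to reproduce.

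**Step 1: order of events.** Appendix 1 of the protocol, notes 2 and 3, allows consent to be signed only once all RB-US-13-0003 EOS assessments are complete, and requires screening and the Day 1 injection on that same day. An AE ongoing at the EOS visit therefore began before the injection.

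**Step 2: apply SAP 20.7 to a carried-over AE.** Illustrative first dose 15 Mar 2017:

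| Recorded start | Imputed start | Position |
|---|---|---|
| Mar 2017, day missing | 15 Mar 2017 | first-dose date |
| Feb 2017, day missing | 28 Feb 2017 | pre-dose |
| 2017 only | 15 Mar 2017 | first-dose date |
| 2016 only | 31 Dec 2016 | pre-dose |
| Missing, stop 10 Apr 2017 | 15 Mar 2017 | first-dose date |
| Missing, stop on 15 Mar 2017 or no stop date | no rule applies | undefined |

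**Step 3: share moved, given that the date is incomplete.** Assumptions, not in the documents: first doses spread evenly over the 365 days of 2017, and true onset uniform over the W days before first dose. Protocol 1.1 gives a maximum of 6 or 12 injections in RB-US-13-0003. At 28 days each, that is W = 6 × 28 = 168 or 12 × 28 = 336. W = 28 and 56 stand for recent onsets.

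*Day missing.* With first dose on day d of a month, min(d − 1, W) of the W possible onsets fall in the same month and are moved. For W of at least 30, the sum over 2017 is 7 × 465 + 4 × 435 + 378 = 5,373 (31-day months, 30-day months, February). For W = 28 the cap removes 7 × 3 + 4 × 1 = 25, leaving 5,348. Share = sum / (365 × W).

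*Day and month missing.* With d as day of the year, the sum of min(d − 1, W) is W(W + 1)/2 + W(364 − W). Share = sum / (365 × W).

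| W (days) | Day missing | Day and month missing |
|---|---|---|
| 28 | 5,348/10,220 = 52% | 9,814/10,220 = 96% |
| 56 | 5,373/20,440 = 26% | 18,844/20,440 = 92% |
| 168 | 5,373/61,320 = 9% | 47,124/61,320 = 77% |
| 336 | 5,373/122,640 = 4% | 66,024/122,640 = 54% |

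Where the start date is missing and the stop date is after first dose, the share is 100% by the rule itself.

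**Step 4: from imputed date to TEAE.** SAP 12.1.1 requires onset following the first dose and does not say how an imputed first-dose date, which has no time, is classified. Counting it as treatment-emergent is the natural reading. Otherwise the rule would also drop genuinely new events with incomplete dates, and would serve little purpose.

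**The case against.** A reader might infer that SAP 20.7 sends every missing start date to first dose. It does not: a known earlier month or year, or a stop date before first dose, keeps the event pre-dose. The point is confined to the three cases.

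A reader might also infer that the SAP plainly declares these events TEAEs. It does not. An AE documented as ongoing at roll-over can be read under the pre-existing limb of 12.1.1, and the status of an imputed Day 1 onset is unwritten. This stands as far as it goes: the text has two rules that conflict for these events and does not say which prevails. SAP 20.1 does not settle it. It assigns records collected before the first injection to Screening, which concerns collection time rather than AE onset.

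The rule can be defended as conservative, because it can only over-count TEAEs in a descriptive study, and all AEs are listed anyway. That limits the harm. It does not justify the rule where the order of onset and dose is known.

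Incomplete dates may be rare. Protocol 6.9.3 requires a date of occurrence, 10.7 an explanation for missing data, and 10.11 edit checks and queries. The CRF is not among the documents, so how carried-over start dates are entered cannot be seen. This also stands, and it is why no count is claimed.

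**Conclusion.** The point holds in its limited form. For carried-over AEs in the three cases, SAP 20.7 imputes the first-dose date without exception, and on the natural reading of 12.1.1 they can be counted as TEAEs without worsening.

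The size cannot be computed, because the documents do not say how many carried-over AEs have incomplete start dates. The shares in the tables are conditional on incompleteness and rest on uniform onset and uniform dosing dates.

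A reader might infer a rise of several percentage points in TEAE incidence. For example, suppose 20% to 40% of 300 subjects carry over an AE, and 5% to 20% of those have a date that is moved. That gives 300 × 0.20 × 0.05 = 3 to 300 × 0.40 × 0.20 = 24 subjects, or 1 to 8 points. The documents support neither input. The points also require that no affected subject has another TEAE; if all do, overall incidence does not change. With a 336-day window and only days missing, about 4% of carried-over AEs would move even if every day were missing, which is below the assumed 5%. The effect may well be small. The correction is still worth making because the rule contradicts the SAP's own definition and is cheap to repair.

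**What to change.** Add to SAP 20.7, in substance:

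- An AE recorded as ongoing at the RB-US-13-0003 EOS visit is treated as pre-dose whatever its imputed date. Use the RB-US-13-0003 start date where it is more complete; otherwise impute no later than immediately before the first injection.
- Such an AE is a TEAE only if its severity increases in the Treatment Period. This includes an increase recorded as a separate event, since protocol 6.9.5 documents severity changes that way. The worsened record keeps its own start date and is linked to the carried-over one.
- For all other AEs, an onset imputed to the first-dose date counts as treatment-emergent.

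In the same edit, supply the missing rule for an AE with no start date that has no stop date or stops on the first-dose date, and say whether SAP 20.6 uses imputed dates.

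The cost is one SAP rule, a merge with the RB-US-13-0003 data on the subject number retained under protocol 5.4, and a link between records of the same event. No new data are needed. The merge improves dates only where the earlier database is more complete, but the first bullet works without it.
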